#### Determine the Fate of the NSCs: NSC Persistence

#### Sample Size:

The anticipated sample size is 29 patients: minimum=6; maximum=53 (allowing for 42 patients for dose escalation through 5 possible dose levels of NSCs and 3 dose schedules of irinotecan, estimating ~3 patients to replace unevaluable/ineligible patients and an additional 8 patients for the expansion cohort).

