### 5.1.2 Phase I Cohorts and Dose Escalation and De-escalation Criteria

Phase I Cohorts will be of 3 or 6 participants, as indicated by the dose-escalation criteria.

**Enrollment of the first 3 patients to a dose level will be staggered** by requiring that each of the first 3 patients be separately observed for 4 weeks (or until the DLT assessment period has ended) before the next patient can start treatment on that dose level.

Dose escalation will proceed through the identified doses without skipping any dose levels.

**To be counted for dose escalation**, a study patient must receive at least 80% of the assigned NSCs and 80% of the irinotecan for a particular dose level and be followed for 4 weeks OR have experienced a DLT as defined in Section 5.3.3.

All study patients enrolled are to be fully followed for toxicity; any study participant who is not evaluable for dose escalation will be replaced.

The NSC dose levels and irinotecan dose schedules are provided in Table 5.3.1. The first cohort will start at NSC dose level 1 and irinotecan schedule A.

The following dose escalation rules will be used, using the DLT definition as provided in Section 5.3.2:

- If 0/3 study participants experiences a DLT, the next cohort of 3 study patients will be treated at the next higher dose level.
- If 1/3 study participants experiences a DLT, the cohort will be expanded by another 3 study participants who will be treated at the same dose level for a total of 6 study participants.
- If 1/6 participants experiences a DLT, the next cohort of 3 study participants will be treated at the next higher dose level.
- If 2 or more participants of either a 3 participant or 6 participant cohort encounter a DLT, then the MTD has been exceeded. If applicable, three (more) participants will be enrolled at the next lower dose level.
- At least 6 patients will be treated at the MTD (or MFD, if the MTD is not reached).

If the 3+3 design rules indicate a need for de-escalation, the following will apply:

- If all DLTs in a dose level are attributed uniquely to irinotecan, then only the irinotecan schedule will de-escalate.
- If all DLTs in a dose level are attributed uniquely to NSCs, and are not attributed to 'NSCs with irinotecan', nor to irinotecan alone, then only the NSC dose level will de-escalate.

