#### 5.1.4 Definition of Maximum Tolerated Dose and Maximum Feasible Dose

---

The MTD/MFD will be based on the assessment of DLTs as defined in Section 5.3.3. The MTD is the dose level at which 0/6 or 1/6 participants experience a DLT with the next higher dose having at least 2/3 or 2/6 participants encountering a DLT. If the MTD has not been reached with NSC dose level 4 and irinotecan schedule A, then that dose level will be termed the maximum feasible dose (MFD).

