#### **Treatment Plan: Expansion Cohort**

---

After the MTD/MFD of the combination therapy is defined, an expansion cohort of 8 patients will be treated to gain more experience regarding the tolerability of study treatment at the MTD/MFD and to assess the biological activity of the hCE1m6-NSCs using intracerebral microdialysis. Since it is anticipated that the MTD/MFD will be 150 million NSCs (dose level 4), the 6 patients who will be treated on dose level 4 will undergo intracerebral microdialysis and be counted as part of the expansion cohort.

Four patients in the expansion cohort will undergo intracerebral microdialysis after receiving NSCs at the time of surgery followed 2 days later by IV irinotecan, but the other 4 patients in this cohort will not receive NSCs on the day of surgery. Instead they will be given IV irinotecan 2 days after surgery, and dialysate samples will be collected from them to determine how much SN-38 is present in the brain from treatment with IV irinotecan alone. These 4 patients will then receive their first dose of NSCs through the Rickham on day 15 of cycle 1 followed by irinotecan on day 17.

To determine who will receive their initial NSCs administration on the day of surgery, and who will receive their first NSC administration on Day 15 via the Rickham catheter, participants will be stratified according to surgery type (craniotomy or biopsy), and, as each group enrolls participants, it will alternate between enrolling the participant to the Day 1 NSC start date and the Day 15 NSC start date. For example, the first craniotomy participant will be assigned Day 1 NSC start date, the second craniotomy participant will be assigned Day 15 NSC start date, the third will be assigned Day 1 NSC start date, the fourth will be assigned Day 15 NSC start date, and so on as applicable. The same alternate enrollment scheme will apply to participants undergoing the biopsy procedure. The rationale for this plan is to ensure to the degree possible an even distribution of start dates for each surgery group which should increase the ability for direct comparison. There is no requirement for specific number of biopsy or craniotomy participants in the expansion cohort.

If the DLT rate in the expansion cohort exceeds 34%, the toxicity data will be reviewed.

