### Sample Size

---

The anticipated sample size is 29patients: minimum=6; maximum= 53(allowing for 42 patients for dose escalation through 5 possible dose levels of NSCs and 3 dose schedules of irinotecan, estimating ~3 patients to replace unevaluable/ineligible patients and an additional 8 patients for the expansion cohort).A sample size of 6 at the MTD/MFD will allow us to i) achieve a maximum margin of error for a 95% confidence interval for the DLT rate of 0.38 and ii) detect a 0.25 toxicity rate in approximately 82% of trials. The additional 8 patients in the expansion cohort, for a total of 14 patients treated at the MTD/MFD, will allow us to i) achieve a maximum margin of error for a 95% confidence interval for the DLT rate of 0.27 and ii) detect a 0.15toxicity rate in approximately 90% of trials.

An important purpose of the expansion cohort is to obtain information about the biologic activity of the hCE1m6-NSCs using intracerebral microdialysis. Sample size calculations based on preclinical results for the AUC from 0 to 20 hours (nMxhr) for SN38in rats (the combination therapy group mean= 7, sd=4.4; irinotecan alone mean=1.8, sd=1.2) implementing a natural log scale (mean difference 1.36 and sd=0.66) indicate 4 participants per group could provided 80% power todetermine if the addition of NSCs to treatment with irinotecan increases intracerebral concentrations of SN-38, using a one-sided two-sample t test with a 0.05 level of significance. As we expect our patient data to be more variable than the preclinical rat data we consider these results to be exploratory.

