### Accrual Rate

---

Given that the first 3 patients entering a cohort until the MTD/MFD is determined will enter sequentially after the prior patient completes cycle 1, the study time is mostly determined by cycle length. It is anticipated that this study will complete accrual within approximately 36 months.

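### The protocol gives two totals for the expected MTD/MFD dose: the expansion-cohort text counts the six level-4 patients among the 8, while Section 15.1 adds 8 to reach 14, and the stated DLT precision holds only at 14

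*Combined protocol and SAP*

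**What the plan says.** The expansion-cohort text (Section 5.4) sets a cohort of 8 at the MTD/MFD. It then says that, because level 4 is expected to be that dose, "the 6 patients who will be treated on dose level 4 will undergo intracerebral microdialysis and be counted as part of the expansion cohort". Section 5.2 (item 5) and footnote d of the dose escalation schema repeat this. Four of the 8 receive NSCs at surgery and four receive their first NSCs on Day 15.

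The sample size text counts differently. The synopsis builds the maximum of 53 from 42 escalation patients, about 3 replacements "and an additional 8 patients for the expansion cohort". Section 15.1 does the same and continues: "The additional 8 patients in the expansion cohort, for a total of 14 patients treated at the MTD/MFD". From that total it claims to "achieve a maximum margin of error for a 95% confidence interval for the DLT rate of 0.27" and to detect a 0.15 toxicity rate in about 90% of trials.

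Three other provisions matter:
- Section 5.4: "If the DLT rate in the expansion cohort exceeds 34%, the toxicity data will be reviewed". It gives no timing and does not say which patients form the denominator.
- Section 5.3.4 (printed as 5.1.4): "The MTD is the dose level at which 0/6 or 1/6 participants experience a DLT", so a dose enters expansion with at most one DLT in six.
- Section 5.3.2 (printed as 5.1.2): to count for escalation without having had a DLT, "a study patient must receive at least 80% of the assigned NSCs and 80% of the irinotecan for a particular dose level". Four weeks of follow-up are also required.

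**The concern.** If level 4 becomes the MTD/MFD, which the protocol expects, the text does not say how many patients to enrol there. A literal reading of Sections 5.2 and 5.4 gives six plus two, or 8 in total. Section 15.1 gives six plus eight, or 14. The analysis plan in Section 15.3 estimates the DLT rate at the RP2D with Clopper-Pearson limits, and that estimate serves the primary objective. Its precision depends on which total applies.

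There is also an intermediate total. The cohort needs four Day-15 starters. Such a patient receives one of the two cycle-1 NSC doses, about 50% if both count as assigned, and so may not meet the 80% rule for the six escalation patients. The four would then have to be new, giving ten patients at the dose.

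The same ambiguity reaches the 34% review, because the count decides which patients enter the rate and how early the threshold can be passed.

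**Working it through.** **Inputs.** Six patients with 0 or 1 DLT at the MTD/MFD (Section 5.3.4); cohort of 8 and threshold above 34% (Section 5.4); 8 additional patients, 14 in total, margin 0.27 and detection 90% (Section 15.1); Clopper-Pearson limits (Section 15.3).

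**Step 1: reproduce the plan's figures.** The margin is the largest half-width of the exact 95% interval, reached at x = n/2. The limits are the 0.025 quantile of Beta(x, n−x+1) and the 0.975 quantile of Beta(x+1, n−x). Detection is the chance of at least one event, 1 − (1−q)^n.
- n = 6: limits 0.118 to 0.882, margin 0.382; 1 − 0.75^6 = 0.822. Stated: 0.38 and 82% for a 0.25 rate.
- n = 14: limits 0.230 to 0.770, margin 0.270; 1 − 0.85^14 = 0.897. Stated: 0.27 and 90% for a 0.15 rate.

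Both pairs match. The Wald margin, 1.96 × √(0.25/n), gives 0.400 and 0.262 and does not.

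**Step 2: the same formulas at the other totals.**

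| Reading at level 4 | Total at MTD/MFD | Margin | Detection of 0.15 |
|---|---|---|---|
| Six plus two new | 8 | 0.343 | 1 − 0.85^8 = 0.728 |
| Four new Day-15 starters needed | 10 | 0.313 | 1 − 0.85^10 = 0.803 |
| Eight additional | 14 | 0.270 | 0.897 |

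With 8 patients, 90% detection is reached only for a 0.25 toxicity (1 − 0.75^8 = 0.900).

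**Step 3: when the 34% threshold can be passed after the dose is cleared.**
- Six plus two. After 0/6 the rate peaks at 2/8 = 25%. After 1/6 it is at most 2/7 = 28.6%, then 3/8 = 37.5%. It passes 34% only if both new patients have a DLT, so after the last patient.
- Six plus four (a cohort of 10). After 1/6, DLTs in the first two new patients give 3/8 with two patients still to come. 3/9 = 33.3% does not pass; 4/10 = 40% does.
- Four of the six plus four new (a cohort of 8, ten at the dose). After 1/4, a DLT in the first new patient gives 2/5 = 40%.
- Eight additional. A running rate can pass at 1/1 or 1/2; a single look at the end needs 3/8.

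**Step 4: how often, for six plus two.** For true DLT rate p, P(cleared) = (1−p)^6 + 6p(1−p)^5, and w = 6p(1−p)^5 / P(cleared) is the share cleared with one DLT. The chance of a review is w × p².

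| p | P(cleared) | w | w × p² |
|---|---|---|---|
| 0.33 | 0.358 | 0.747 | 0.081 |
| 0.40 | 0.233 | 0.800 | 0.128 |
| 0.50 | 0.109 | 0.857 | 0.214 |

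Enumerating the new patients in the other readings, with the rate checked at each DLT, gives the chance that the threshold is ever met at p = 0.33, 0.40 and 0.50. It is 12%, 19% and 33% for six plus four; 30%, 41% and 56% for four plus four; and 72%, 83% and 93% for eight additional. If eight additional patients are looked at once, at the end, it is 52%, 69% and 86%.

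**The case against.** The strongest reply is that the review rule is barely affected. A reader might infer that the expansion-cohort text makes the 34% review fire only after the last patient. The documents do not support that in general. It is true of six plus two, but that reading may be unable to supply the four Day-15 starters that Section 5.4 itself requires, given the 80% rule. With four new patients the threshold can be met before the last one. The high figures for eight additional patients should not be oversold either: checked at every DLT, that rule also fires 34% of the time at a true rate of 0.15, because a single early DLT is enough.

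A reader might also infer a serious safety gap. The rule prompts a data review and is not a stopping rule. Nothing in Section 5.4 bars an earlier review. Protocol team monitoring, quarterly DSMC reports and expedited reporting of serious events continue (Section 11). Section 5.6 still applies, although its threshold is higher (over 50%, in more than 6 patients, with probable or definite attribution).

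These replies stand, and they limit the point about the review. They do not resolve the conflict between 8 additional patients and six already counted, or its effect on precision. It is also true that the conflict does not arise in this form if the MTD is below level 4: the six level-4 patients are then not at the MTD, and 8 new patients give 14.

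**Conclusion.** The inconsistency is real and lies on the path the protocol expects. If level 4 is the MTD/MFD and the six are counted, the stated 0.27 and 90% are not delivered. They become 0.34 and 73% with 8 patients at the dose, or 0.31 and 80% with 10. The Section 15.1 calculations are correct for 14 patients; a reader who took them to be wrong would be mistaken.

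For the 34% review, the finding is that its denominator is undefined. On six plus two it can be met only at 3/8, after the last patient; on the other readings it can be met earlier. The safety effect is modest.

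This rests on level 4 being the MTD/MFD, on detection meaning at least one event (which reproduces the stated figures), and on the rate being taken once the dose is declared. Before then the 3+3 rules govern. The total of 10 also assumes that both cycle-1 NSC doses count as assigned under the 80% rule.

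**What to change.** State in Section 5.4, and in its repeats in Section 5.2 and schema footnote d, whether the 8 expansion patients are additional to the six at level 4.

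- If additional: delete the sentence that counts the six and keep the Section 15.1 figures. The maximum does not change, since 42 + 3 + 8 = 53 already includes them. The cost is six more patients treated than under six plus two, or four more than with four new patients.
- If the six are counted: state how many new patients are enrolled so that four Day-15 starters are available, and restate Section 15.1 for the resulting total (8: 0.34 and 73%; 10: 0.31 and 80%). The additional-patient wording and the maximum in the synopsis and Section 15.1 then need to match. The cost is lower stated precision.

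In either case, name the patients who form the denominator of the 34% review. This is a text edit.

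Assessing the rate at each DLT, holding enrolment during a review, or staggering the new patients are optional. They do not follow from the counting conflict, and Section 15.2 applies sequential entry only to "the first 3 patients entering a cohort until the MTD/MFD is determined will enter sequentially after the prior patient completes cycle 1". Each staggered wait would add about 4 weeks.

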#### **Criteria for Removal from Participation or Treatment**

---

For participants who begin treatment, duration of therapy will depend on individual response, evidence of disease progression and tolerance. In the absence of treatment delays due to adverse events, treatment may begin and continue until or unless one of the following criteria applies:

- Pathology review of the frozen section obtained at the time of surgery does not confirm recurrent high grade glioma (Section 8.1). Such participants will not continue on to receive any study agents, and all study procedures will end.

- Participant does not meet the criteria for initiating irinotecan dosing following surgery (Section 7.2.3). During cycle 1, if a participant requires more than 16 mg/day of dexamethasone to control cerebral edema at the time s/he is ready to begin treatment with irinotecan, then s/he will be considered neurologically unstable and will not continue with study treatment; however, the patient will still be evaluable for toxicity.
- Evidence of disease progression.
- Unacceptable adverse event(s) (see Section 7.2).
- Intercurrent illness that prevents further administration of treatment.
- Participant needs a treatment not allowed by the protocol.
- A participant may always be removed from treatment whenever s/he wishes.
- General or specific changes in the participant's condition render the participant unacceptable for further treatment in the opinion of the treating investigator.

Participants will be removed from study treatment when any one of the criteria listed above applies. The reason for study treatment removal and the date the participant was removed must be documented. Alternative care options will be discussed with the participant.

### **Study Stopping Rules**

The study will be discontinued if i) the incidence of DLT level toxicities that are probably or definitely attributable to the NSCs or NSCs and irinotecan in study patients exceeds 50% in more than 6 patients, or ii) two grade 4 allergic reactions that are probably or definitely related to NSCs. Note death from tumor progression will be scored as a grade 5 toxicity (with very low level of attribution—unlikely or not related), and only deaths occurring < 30 days from intracerebral administration of NSCs will be considered for the purposes of defining conditions for discontinuation of the study.

### **Subject Follow-Up**

Patients will continue to be followed once they have finished active study treatment. They will be asked to participate in long-term follow-up per the guidelines set forth by the FDA's Biological Response Modifiers Advisory Committee (BRMAC) that apply to gene transfer studies. Current recommendations from the BRMAC require a minimum of 15 years of follow-up. This long-term follow-up will consist of annual requests from the patient/patient's primary oncologist for clinical information regarding other anti-cancer therapy, progression of disease, survival, as well as information pertaining to *de novo* cancer, neurologic, autoimmune and hematologic disorders. In addition, unexpected medical problems including information on hospitalizations and medications will be collected. Alternatively, participants may be seen at the COH clinic to obtain this information.

Testing for replication competent retrovirus (RCR) will be part of the long-term follow-up of study patients and will be performed by analysis of DNA from whole blood by PCR for RCR-specific sequences at the following time points: pre-treatment, 3 months, 6 months, 1 year, and annually thereafter.

## 6 CONCOMITANT MEDICATIONS, SUPPORTIVE CARE, AND INCREASED MONITORING FOLLOWING TOXICITIES

---

### 6.1 Prophylaxis, Supportive Treatment and Increased Monitoring

---

Unless expressly indicated elsewhere in this section, increased monitoring, prophylaxis, and ancillary treatment after any toxicity is left to the clinical judgment of the investigator and must be compliant with Section 6.2 Concomitant Medications.

#### 6.1.1 REQUIRED Peri- and post-operative Prophylaxis

---

Levetiracetem (Keppra)—or another anticonvulsant that does not cause significant induction of hepatic metabolic enzymes, such as lacosamide or valproic acid—will be administered to all study patients. Those who have never had a seizure will start taking levetiracetam within 1 week prior to surgery and continue taking the anti-seizure medication for 4 weeks after craniotomy or biopsy.

Peri-operative antibiotics, corticosteroids, and deep vein thrombosis prophylaxis will be used according to the standard of care for the surgical procedure.

For participants with microdialysis catheters, prophylactic antibiotic use will continue as long as the microdialysis catheter(s) remains in place.

#### 6.1.2 REQUIRED Catheter Infection Prophylaxis and Monitoring for Infection

---

Also, to monitor for possible catheter-related infections, an attempt to aspirate fluid from the Rickham reservoir will be done prior to administering a dose of hCE1m6-NSCs. The fluid will be sent for culture, as well as routine cell count, glucose and protein levels, depending on the amount of fluid obtained.

A 14 day culture for bacteria and a 28 day culture for fungus will be started on every final NSC product. The NSC product will be administered to the study patient before the results of the sterility testing are known. If these culture results were to become positive for bacteria, or fungus, then an Infectious Diseases consultation would be obtained for recommendations regarding appropriate treatment of the isolate that grows out.

#### 6.1.3 REQUIRED Nausea Prophylaxis, Participant Education, and Treatment

---

Participants will be pre-medicated with ondansetron 16 mg p.o. at least 30 minutes prior to each infusion of irinotecan.

Additional use of anti-emetics is at the discretion of the investigator.

#### 6.1.4 REQUIRED Diarrhea Treatment and Participant Education

---

Diarrhea is a common side effect of irinotecan, and aggressive management with anti-diarrheal agents is necessary. All study patients will be counseled about the importance of early recognition and treatment of diarrhea.

Orders will be written for standard use of atropine (to prevent early onset diarrhea) and loperamide (for management of later diarrhea) as needed. Prophylactic use of atropine to prevent early onset diarrhea accompanied by cholinergic symptoms is left to investigator discretion.

Each patient should be instructed to have loperamide readily available and to begin treatment for diarrhea at the first episode of poorly formed or loose stools or the earliest onset of bowel movements more frequent than normally expected for the patient. Loperamide 4 mg should be taken at the first loose stool or more frequent

than usual bowel movements, followed by 2 mg as needed, no more frequently than every 4 hours not to exceed a total of 16 mg in 24 hours. If the diarrhea persists (> grade 1) despite use of loperamide, then s/he should start taking diphenoxylate/atropine (Lomotil) 2 tablets every 6 hours.

#### **6.1.5 REQUIRED Increased Monitoring following Initial Indications of Possible Immune Response to the NSCs**

If a patient starts exhibiting signs/symptoms concerning for a possible immune response to the NSCs (such as development of a new neurologic deficit that cannot be attributed to the location of the patient's brain tumor, fever without a localizing source of infection, or rash not likely due to a concomitant medication), then **serum samples will be collected from the patient as soon as possible, and if feasible without putting the participant at increased risk, prior to administration of supportive care. A second sample, and additional samples if possible, should be taken approximately every 2 days to determine response to supportive care for the immune response.** The patient's stored serum samples from prior to start of study treatment, will also be analyzed for the same cytokine panel. See Section 8.6 for blood collection information.

In particular, we would be looking for changes in levels of IL-1RA, IL-6, IFN- $\gamma$ , IP-10, MIP-1 $\beta$ , MCP-1, IL-2RA, IL-8, IL-10, MIP-1 $\alpha$ , G-CSF, IL-15, IL-7, IL-2, TNF- $\alpha$ , IL-1 $\beta$ . Findings consistent with the presence of a "cytokine storm" would add strength to the conclusion that the patient is experiencing an immune reaction to the NSCs. See Section 12.2.5 for additional information regarding the cytokine panel.

A decision to stop study treatment will be based on development of clinical signs/symptoms of an immune response rather than a particular level of anti-NSC T cells or antibodies.

See Section 6.1.5 for required supportive care.

